1.1 Study Objectives

Describe the purpose, specific aims or objectives. State the hypotheses to be tested.

The objective of this study is to evaluate the effectiveness of oral naltrexone tablets in pediatric and adolescent eating disorders, in particular anorexia nervosa and bulimia nervosa, as compared to placebo. The hypothesis of this study is that patients receiving oral naltrexone will demonstrate greater improvement in their score on the ED-15, an evidence-based metric of eating disorder symptom severity and frequency¹, than those receiving placebo, representing more complete recovery from eating disorder

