1.2 Primary Study Endpoints

State the primary endpoints to be measured in the study.

Clinical trials typically have a primary objective or endpoint. Additional objectives and endpoints are secondary. The endpoints (or outcomes), determined for each study subject, are the quantitative measurements required by the objectives. Measuring the selected endpoints is the goal of a trial (examples: response rate and survival).

The primary outcome will be clinically and statistically significant reduction in ED-15 score in those receiving medication vs placebo.

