7.1 Study Design

Describe and explain the study design.

This is a double-blind, randomized, placebo-controlled study. We have developed the following schedule of events. All events with a superscript $^{\circ}$ are for study purposes only and are not part of the standard of care:

	Pre-Enrollment Screening: Medical	Enrollment	Week 1	Week 2	Week 3	Week 4	Week 5	Week 6 (end of treatment	Week 8-9 (post- treatment)	Six Months
Intervention								_	>	
Initial Medical Assessment	Х									
Subsequent Medical Assessment, including comprehensive review of systems			x		x		x		х	х
Initial Psychiatry Assessment	X									
Subsequent Psychiatric Assessment, including suicidal ideation			х	х	х	х	х	х	х	х
Discussion of risks and benefits, inclusion and exclusion criteria ^o		х								
Consent/Assent ^o		Х								
\$25 Greenphire Clincardo		Х								х
Urine Drug Screen ^o		Х								
Serum Pregnancy Test (female participants)°		х								
Urine Pregnancy Test (female participants)°					х			х		
Administer Study Article ^o			Х	Х	х	Х	Х	х		
EKG	X									
AST	X				Xº			Xº		
ALT	Х				χ°			Xo		
Total Bilirubin	Х				Xº			Xº		
Direct bilirubin	Х				Xº			Xº		
Heart Rate	Х		Х	Х	Х	Х	Х	Х	Х	Х
BMI	X		Х	Х	Х	Х	Х	X	Х	Х
Height	X		Х	X	X	X	Х	X	X	Х
Weight	X		X	X	X	X	X	X	X	X
Blood Pressure	X		X	X	X	X	X	X	X	X
Temperature Adverse event monitoring ^o	Х		X	x	x	x	x	x	X	X
Suicidal Ideation Screening (ASQ			^	^	^	^	^			
for age <17or C-SSRS for age 18+)		х	Х	Х	х	Х	Х	х	Х	Х
ED-15		Х	х		х			Х	X	х
EDE-Q		Х	х		х			Х	X	Х
ABUSI°		Х	Х		х			Х	Х	Х
GAD-7		Х	х		х			Х	Х	Х
PHQ-9		Х	Х		Х			Х	X	Х
BIS/BAS°		Х	Х		Х			Х	Х	Х

Note: Medical assessments may occur in weeks 1,3 etc or 2,4 etc depending on standard of care for that patient. As long as patients are seen within a 14 day interval (2 week timeframe), the exact week intervals (1,3 or 2,4) may vary. Additionally, the 6 month follow up appointment may take place any time between 5-7 months after study enrollment ends.

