7.2 Duration of Participation

Describe how long subjects will be involved in this research study. Include the number of sessions and the duration of each session - consider the total number of minutes, hours, days, months, years, etc.

Subjects will be enrolled in this study for a total of six months, starting at enrollment in PHP, and continuing to their final 6-month follow-up visit. They will have study interventions at 0, 3, and 6 weeks, and again at six months. They will take study medication while in PHP, and stop once six weeks of study duration is completed. Duration of PHP is individualized, but is on average about 8 weeks. Duration of PHP will not be dependent upon study participation.

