7.3.3 Method for Assigning Subject to Treatment Groups

Describe the randomization process and how the associated treatment assignment will be made.

Subjects will be randomized at enrollment using RedCap. Randomization will be stratified by age (16 and under or 17 and older) and diagnosis (anorexia nervosa binge/purge subtype and bulimia nervosa or OSFED with bingeing or purging behaviors), equaling 4 strata.

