8.3 Statistical methods

Describe the statistical methods (or non-statistical methods of analysis) that will be employed.

For analysis, data will be analyzed for differences between participants receiving naltrexone and participants receiving placebo. The data will be analyzed for demography differences between the two groups at baseline, and outcomes will be compared at three and six weeks; as well as at 6 months. Outcomes to be compared are stated in section 1.1 and 1.2. Within each group, these outcomes will also be compared across time. Statistically significant differences between each group at each endpoint will be noted and reported.

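### The primary ED-15 outcome has no deciding timepoint and no number for clinical significance, while section 8.3 compares the arms at three unranked times

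*Combined protocol and SAP*

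**What the plan says.** The hypothesis in section 1.1 is that "patients receiving oral naltrexone will demonstrate greater improvement in their score on the ED-15" than those on placebo. No time is attached. Section 1.2 turns this into the endpoint: "The primary outcome will be clinically and statistically significant reduction in ED-15 score in those receiving medication vs placebo". Again there is no time, and no ED-15 value is given, here or elsewhere, for a clinically significant reduction. Table 1 in section 1.0 lists the primary endpoint simply as the ED-15 score.

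The analysis is in section 8.3: "outcomes will be compared at three and six weeks; as well as at 6 months", followed by "Statistically significant differences between each group at each endpoint will be noted and reported". None of the three times is called primary. No test, significance level or rule for multiple comparisons is stated. For the list of outcomes it says "Outcomes to be compared are stated in section 1.1 and 1.2", although the secondary outcomes are in section 1.3.

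The schedule in section 7.1 collects the ED-15 at enrollment, at weeks 1, 3, 6 and 8-9, and at six months. It labels one column "Week 6 (end of treatment", but nothing makes that visit the one that decides the primary question. Sections 8.1 and 8.2 describe the trial as a pilot with 30 participants per arm, a number set by what can be recruited in 18 months.

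**The concern.** The primary outcome is defined by a significance result, so the plan must say which result. It offers three and does not choose. It sets no rule that one significant time out of three is enough. Nor does it exclude presenting one as a positive primary finding.

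The three times ask different questions. On the schedule, weeks 3 and 6 fall within treatment and 6 months falls well after it. Whether open-label naltrexone could begin before the 6-month ED-15 is also unclear. Section 7.3.2 offers it once the study is complete, while section 7.2 (Duration of Participation) has participants in the study and "continuing to their final 6-month follow-up visit". A benefit at week 6 that has gone by 6 months is a quite possible pattern, and under this plan it could be reported as a success or as a failure.

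The undefined clinical criterion adds a second open choice. Without an ED-15 number, whether a significant difference is also clinically significant would be judged after the result is known.

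**Working it through.** There is no figure in the plan to reproduce: no significance level, power, effect size or SD is given, and the total of 60 rests on feasibility. The check therefore asks what false-positive rates the text allows.

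**Inputs.** Three between-arm ED-15 comparisons (section 8.3) and 30 per arm (section 8.1). Assumed, because not stated: two-sided 5% tests (critical value 1.96) and an equal correlation ρ between the three test statistics, from 0 to 0.9.

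**Formulas.** Under no effect, write each statistic as √ρ·u + √(1−ρ)·e, with u and e standard normal. For results favouring naltrexone, the direction section 1.2 requires:

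- any one of three: 1 − ∫ Φ((1.96 − √ρ·u)/√(1−ρ))³ φ(u) du
- all three: ∫ Φ((√ρ·u − 1.96)/√(1−ρ))³ φ(u) du

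At ρ = 0 these reduce to 1 − 0.975³ = 0.0731 and 0.025³ = 0.00002. In either direction, any-one is 1 − 0.95³ = 0.1426.

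| ρ | Any one, favouring naltrexone | All three, favouring naltrexone | Any one, either direction |
|---|---|---|---|
| 0 | 7.3% | under 0.01% | 14.3% |
| 0.5 | 6.3% | 0.2% | 12.5% |
| 0.7 | 5.5% | 0.4% | 10.9% |
| 0.9 | 4.2% | 1.1% | 8.4% |
| One named time | 2.5% | 2.5% | 5% |

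Simulated two-sample t-tests with 30 per arm agree with both any-one columns to within about 0.2 percentage points. With unequal correlations (0.7 between weeks 3 and 6, 0.4 between each of these and 6 months), the any-one rate favouring naltrexone is 6.2%.

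**Precision of one week-6 comparison.** With 30 scores per arm the unadjusted 95% CI half-width is t(0.975, 58) × √(2/30) = 0.52 SD. Let r be the enrollment-to-week-6 correlation, assumed to be 0.3, 0.5 or 0.7. Analysing change scores multiplies the half-width by √(2(1−r)); adjusting for the enrollment score multiplies it by √(1−r²), ignoring a small loss of degrees of freedom.

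| r | Change score | Adjusted for enrollment ED-15 |
|---|---|---|
| 0.3 | 0.61 SD | 0.49 SD |
| 0.5 | 0.52 SD | 0.45 SD |
| 0.7 | 0.40 SD | 0.37 SD |

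**One time or all three with a correction.** By normal approximation, unadjusted and without dropout, the difference detectable with 80% power is (1.96 + 0.84) × √(2/30) = 0.72 SD for a single 5% test. Splitting the 5% over three times (1.67% each) raises it to 0.84 SD, and power at 0.5 SD falls from 49% to 32%. Naming one time is therefore the better use of 60 participants.

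**The case against.** The strongest reply is that the inflation is hypothetical. Neither the any-one nor the all-three rule is in the plan, and the significance level and correlations are assumed. A clinical threshold on top of significance would lower every rate shown. This is right as far as it goes: the text shows that the error rate is undefined, not that it is inflated. The figures only show how far apart the permitted readings lie.

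Second, context points to week 6. It carries the end-of-treatment label, and the 6-month weights are described as a check on whether weight restoration lasted. A reader might well infer week 6, but section 8.3 gives 6 months equal standing.

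Third, this is a pilot and section 8.3 may be meant descriptively. That lowers the stakes, but sections 1.1 and 1.2 still set an efficacy hypothesis and a significance-based outcome, with no feasibility endpoint in their place. The sentence about each endpoint might also refer to each scale and not each time; the three times are fixed by the sentence on comparisons in any case.

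Two practical points stand beside the finding. Sections 7.2 (Study Procedures) and 9.2 tie study medication to time in the program, whereas section 7.3.2 continues it to six weeks. Week 6 may therefore be off drug for early completers, and these passages must be reconciled. Section 3.3.2 uses data only up to withdrawal, so some week-6 scores will be missing. At 24 per arm, for illustration, the unadjusted half-width is 0.58 SD instead of 0.52 SD.

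**Conclusion.** The concern holds. Followed exactly, the plan cannot say whether its primary outcome was met when the three times disagree, and it gives no number by which a reduction could be judged clinically significant. Under the assumed two-sided 5% tests and a correlation of 0.7, the false-positive rate favouring naltrexone could lie anywhere from 0.4% to 5.5%, against 2.5% for one named time. The any-one rate exceeds the single-test rate at every correlation examined, and the all-three rate is below it throughout. A stated clinical threshold would lower these figures by an amount that cannot be calculated from the documents. This should be fixed; the pilot setting limits the consequences but does not answer the question.

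**What to change.** Name one primary comparison in sections 1.2 and 8.3, and bring Table 1 into line. For example: the between-arm difference in ED-15 at week 6, by randomised arm, adjusted for enrollment ED-15 and the randomisation strata, with one two-sided 5% test and a 95% CI. The strata are already defined: "Randomization will be stratified by age (16 and under or 17 and older) and diagnosis". With the enrollment score in the model, the arm difference is the same whether the outcome is the week-6 score or the change from enrollment, so this fits the improvement and reduction wording of sections 1.1 and 1.2. If the investigators see a later time as the main question, they should name that one; what matters is that one is fixed in advance. How missing scores at that time are handled should be stated alongside it.

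Take the significance requirement out of the endpoint definition. If a clinically meaningful ED-15 difference is wanted, state it separately as a number for interpretation.

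Make week 3, week 8-9 (collected but absent from section 8.3), 6 months and the section 1.3 outcomes secondary. Report them as estimates with CIs and not as grounds for a positive primary conclusion. Correct the cross-reference in section 8.3 to sections 1.2 and 1.3; it is probably a numbering slip.

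The cost is wording. No visits, measurements or participants are added, because the ED-15 is already scheduled at enrollment and week 6 and the strata are recorded at randomisation. The price is that significance seen only at another time can no longer be called a positive primary result.

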3.3.2 Follow-up for withdrawn subjects

Describe when and how to withdraw subjects from the study; the type and timing of the data to be collected for withdrawal of subjects; whether and how subjects are to be replaced; the follow-up for subjects withdrawn from investigational treatment.

- Patients who are withdrawn from the study will continue with their routine eating disorder
 care at whatever level of care is clinically appropriate for them at that time; that is, they will
 continue with routine care. Data generated from their participation in this study will be used
 to the point of their withdrawal. Specific study subjects do not require replacement.
- Patients who screen positive for opioid substances at enrollment will be provided with a referral for substance use disorder treatment.
- Patients who screen positive for pregnancy will be referred for pregnancy options counseling.

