The subject will be provided with oral naltrexone or placebo weekly from the MSHMC research pharmacy. Subjects will be given one weeks' worth of medication at a time. Subjects will be randomized at enrollment to receive either study drug (naltrexone) or placebo. Participants or parents of minor participants will be provided study drug or placebo following completion of urine drug screen and consent/assent. Patients will take the medication daily while they are in programming; after completion of programming or withdrawal from the study they will no longer be given study medication. For subjects who are enrolled in child PHP and who eat meals with parents, the families may choose to administer study drug during meals at programming. For adult patients enrolled in adult programming, subjects may choose to self-administer the medication.

On their first contact with PHP, all patients in Adult PHP complete various eating disorder indices as a part of routine care, including the ED-15, PHQ-9, GAD-7, and EDE-Q. This battery of indices is repeated every 3 weeks while a patient is in programming.

For those who are enrolled in this study, they will complete their routine indices, in addition they will also complete the BIS/BAS and the ABUSI at enrollment and at weeks 1, 3, and 6 while enrolled in the study. Participants will also be asked to take the routine indices (ED-15, EDE-Q, PHQ, GAD, BIS/BAS, and ABUSI) at week 8 or 9 for a post-treatment evaluation. These will be taken in an in-person medical appointment or electronically via RedCap

6 months after enrollment, subjects will be sent copies of ED-15, EDE-Q, PHQ, GAD, BIS/BAS, and ABUSI indices either in an in-person medical appointment or via RedCap to complete. If the patient returns for medical follow-up between 5 and 7 months after enrollment, their height, weight, and body mass index will also be recorded to determine if weight restoration was maintained.

Patients in Child PHP typically complete a different inventory every three weeks as part of routine care. If a patient choses to participate in this study they will be asked to complete the same surveys as participants in Adult PHP (ED-15, GAD-7, and PHQ-9), and they will receive the same amount and type of compensation as those who already take them as part of standard of care.

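### Section 8.3 gives baseline ED-15, the randomisation strata, the week 8/9 scores and withdrawn participants' partial records no stated role in the between-arm comparison; one baseline-adjusted repeated-measures model would use them all

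*Combined protocol and SAP*

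**What the plan says.** **Analysis.** Section 8.3 looks at demographic differences between the groups at baseline and then states that "outcomes will be compared at three and six weeks; as well as at 6 months". It adds "Within each group, these outcomes will also be compared across time" and "Statistically significant differences between each group at each endpoint will be noted and reported". No test, model, covariate, analysis set, main time point or missing-data method is named. On scope it says "Outcomes to be compared are stated in section 1.1 and 1.2"; the secondary endpoints are in section 1.3.

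**Data collected.** The schedule in section 7.1 marks ED-15 at enrollment, weeks 1, 3 and 6, weeks 8–9 and six months. Section 7.2 (Study Procedures) confirms that all scales are requested "at week 8 or 9 for a post-treatment evaluation". For week 1 the text is narrower: "they will also complete the BIS/BAS and the ABUSI at enrollment and at weeks 1, 3, and 6 while enrolled in the study" concerns only the two added scales, and the routine battery containing ED-15 is described as three-weekly.

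**Design and withdrawal.** Section 7.3.3 stratifies randomisation by age group and diagnosis. Section 3.3.1 removes participants who need a higher level of eating-disorder care or medical hospitalization. Section 3.3.2 keeps their data "to the point of their withdrawal" and does not require replacement.

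**The concern.** The hypothesis in section 1.1 is about improvement, so baseline ED-15 is central, yet 8.3 does not say how it enters the comparison of arms. The strata are also absent from the analysis. The first scores after treatment ends, at week 8/9, are collected but are not among the listed between-arm time points.

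Withdrawal is partly a consequence of doing badly. A participant removed after week 3 may have no week-6 score, and 8.3 does not say how the enrollment and week-3 scores are then used. If the analysis defaults to those with a week-6 score, the poorest outcomes tend to be missing. If that happens more often on placebo because the drug works, the observed difference shrinks. With 60 participants and no power calculation (section 8.2), precision available from data already in hand matters.

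Read literally, the reference to 1.1 and 1.2 also leaves the section 1.3 scales without any analysis.

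**Working it through.** There is no power-based figure to reproduce. The sample size of 2 × 30 = 60 was set for feasibility, and the documents give no alpha, SD, target effect, dropout rate or between-visit correlation. All inputs below other than 30 per arm are assumptions: SD = 1, two-sided 0.05, about 20% loss (24 per arm left), correlation 0.5 to 0.7.

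**1. What the trial can detect without adjustment.** Detectable effect at 80% power = (1.96 + 0.842) × √(2/n).
- n = 30: 2.802 × 0.258 = 0.72 SD
- n = 24: 2.802 × 0.289 = 0.81 SD

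For a true effect of 0.5 SD, power is about 49% with 30 per arm and 41% with 24.

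**2. What baseline adjustment alone gives.** SE(raw) = √(2/n) and SE(ANCOVA) ≈ √(2(1 − ρ²)/n), where ρ is the baseline-to-week-6 correlation. With n = 24:

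| ρ | SE raw | SE ANCOVA | Reduction | Detectable effect |
|---|---|---|---|---|
| 0.5 | 0.289 | 0.250 | 13% | 0.70 SD |
| 0.6 | 0.289 | 0.231 | 20% | 0.65 SD |
| 0.7 | 0.289 | 0.206 | 29% | 0.58 SD |

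**3. Simulation of the repeated-measures model.** 4,000 trials per setting, 30 per arm, true week-6 effect 0.5 SD, loss of about 21% on placebo and 16% on naltrexone driven by the week-3 score. Mean estimate (SE):

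| ρ | Raw, week-6 scores available | Repeated measures | SE reduction |
|---|---|---|---|
| 0.5 | 0.471 (0.279) | 0.501 (0.248) | 11% |
| 0.6 | 0.466 (0.284) | 0.497 (0.234) | 18% |
| 0.7 | 0.451 (0.274) | 0.496 (0.204) | 26% |

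The raw estimate falls short of 0.5 by 0.03–0.05 SD; a second run with similar loss (about 19% and 16%) gave a shortfall of 0.02 SD.

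**4. Against ANCOVA rather than a raw comparison.** In a similar setting (about 21% and 17% loss), completer ANCOVA averaged 0.49 with SE 0.252, 0.239 and 0.207 at ρ = 0.5, 0.6 and 0.7. The repeated-measures estimate averaged 0.50 with SE 0.250, 0.235 and 0.205. The further gain is 1–2% in SE (1–3% if correlation decays over time) and about 0.01 SD in bias. This agrees with step 2: baseline does most of the work.

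**5. Sensitivity to the assumptions.**
- *Correlation falling with distance between visits* (0.5 or 0.7 for adjacent visits), 20% random loss: raw 0.288–0.291, completer ANCOVA 0.251–0.278, model 0.246–0.272. The gain over raw is then 6–15%.
- *No loss:* model and ANCOVA have the same SE (0.246 at 0.5; 0.218 at 0.7) against 0.256 raw.
- *About 21% loss tied to observed scores differently by arm, true effect zero:* absolute bias 0.14–0.19 SD raw, 0.09–0.10 ANCOVA, 0.04 model without week 1, and 0.00 model with week 1.
- *The same, but driven by unobserved scores:* 0.24–0.25 raw, 0.17–0.21 ANCOVA, 0.12–0.17 model. Much of the bias remains.

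The simulations used baseline and weeks 1, 3 and 6. Week 8/9 and month 6 were not simulated.

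**6. Week 1.** The section 7.1 table marks ED-15 at week 1. Section 7.2 (Study Procedures) names week 1 only for BIS/BAS and ABUSI, section 7.1.2 lists those two scales at weeks 3, 6 and 8/9, and Duration of Participation lists weeks 0, 3 and 6 and six months. Whether week-1 ED-15 scores will exist is therefore unsettled.

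**The case against.** The strongest reply is that 8.3 names no method, so there is no wrong method to criticise. A list of comparison times is compatible with visit contrasts from one mixed model.

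A reader might infer that the plan tests the arms separately on whoever has data, ignores dropouts and discards the week-1 and week 8/9 scores. The documents do not support that. Section 8.3 states no analysis set; section 3.3.2 keeps data up to withdrawal; the within-group comparison over time lists no visits and may include both; and section 7.3.2 keeps surveying those who finish PHP early, so finishing the programme is not dropout. Escalation of care is also a secondary endpoint, so those participants are counted there.

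A reader might also infer that a repeated-measures model is in itself clearly more precise and less biased. That is not supported either. Sections 1.1 and 1.2 speak of improvement and reduction, so a raw week-6 comparison is a weak comparator. Against ANCOVA the gain is 1–3% in SE. In one scenario with arm-dependent loss a completer change score was also essentially unbiased, though less precise. An unstructured covariance over five visits has 5 × 6 / 2 = 15 parameters, which is demanding for at most 60 people.

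What remains is narrower. The between-arm plan gives no role to baseline ED-15, strata, week 8/9 or partial records, and its cross-reference misses section 1.3. Pilot status does not remove this, because section 1.2 makes a statistically significant difference the primary outcome.

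**Conclusion.** The point holds as an improvement that costs no new data, not as proof of a wrong analysis. Assuming about 20% loss and a common correlation of 0.5–0.7, a baseline-adjusted repeated-measures model gives an SE roughly 11–26% below an unadjusted week-6 comparison, or 6–15% if correlation falls with time between visits. Nearly all of this is baseline adjustment.

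The bias gain is 0.02–0.05 SD against the raw comparison in the main simulated case and about 0.01 SD against ANCOVA. It is larger only if withdrawal depends on observed scores differently by arm. Where withdrawal follows worsening that no survey captured, which removal for escalation of care may well do, the model does not remove the bias and a sensitivity analysis is needed. The cross-reference slip and the week-1 inconsistency can be verified from the text and rest on no assumption.

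**What to change.** In section 8.3:

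1. Specify one repeated-measures model on all randomised participants, using ED-15 at every post-baseline visit collected (weeks 3, 6 and 8/9 and month 6, plus week 1 if confirmed). Fixed effects: arm, visit, arm-by-visit, baseline ED-15, age group and diagnosis.
2. Use an unstructured covariance with a small-sample degrees-of-freedom method such as Kenward–Roger, and name in advance a simpler covariance to use if it does not converge.
3. Report the week-6 arm difference with its 95% CI as the main result, and week 8/9 as the off-drug contrast.
4. Apply the same model to the section 1.3 scales and change the cross-reference to 1.2 and 1.3.
5. Add a sensitivity analysis that gives participants removed for escalation of care an unfavourable week-6 value, with the value or its rule written down beforehand.
6. Reconcile the section 7.1 table with the text of 7.2 (Study Procedures), 7.1.2 and Duration of Participation on whether ED-15 is collected at week 1.

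The cost is plan wording and slightly more analysis work. No new data are needed, and the sample size and visit schedule can stay as they are apart from settling week 1.

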1.0 Objectives

Table 1: Objectives, Endpoints, and Justifications					
Objectives	Endpoints	Justification			
Primary	Primary	Primary			
Evaluate the effectiveness of	ED-15 score	ED-15 is an evidenced-based			
oral naltrexone tablets in		metric of eating disorder			
pediatric and adolescent eating		symptom severity and			
disorders, particularly anorexia		frequency.			
nervosa and bulimia nervosa, as					
compared to placebo.					
Secondary	Secondary	Secondary			
Evaluate the effect of oral	Improvement on Eating	Naltrexone has some effect on			
naltrexone on desire to self-	Disorder Examination	desire to self-harm, and this can			
harm and impulsivity in patients	Questionnaire (EDE-Q), Patient	be examined in eating disorder			
with eating disorders	Health Questionnaire-9 (PHQ-	patients. EDE-Q, GAD-7, PHQ-			
	9), Generalized Anxiety	and BIS/BAS measure other			
	Disorder-7 (GAD-7), Alexian	features of eating disorder			
	Brothers Urge to Self-Injury				
	Scale (ABUSI), and Behavioral				
	Inhibition System/Behavioral				
	Activation System score				
	(BIS/BAS), need for escalation of				
	level of care, desire to restart				
	study article, and rate of weight				
	restoration.				
Tertiary/Exploratory	Tertiary/Exploratory	Tertiary/Exploratory			
none					

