1.3 Secondary Study Endpoints

State the secondary endpoints to be measured in the study.

Secondary outcomes will include improvement in scores on Eating Disorder Examination Questionnaire (EDE-Q)², the Patient Health Questionnaire-9 scale (PHQ-9,, a measure of depression)³ the Generalized Anxiety Disorder-7 scale(GAD-7, an inventory of anxiety)⁴, Alexian Brothers Urge to Self-Injure Scale (ABUSI; an inventory measuring the desire to self-harm)⁵, and Behavioral Inhibition System/Behavioral Activation System score (BIS/BAS; an impulsivity inventory)⁶; need for escalation of level of care (such as requirement for early termination of partial hospitalization program to attend inpatient or residential eating disorder care or hospitalization for medical stabilization); and rate of weight restoration.

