11.2 Potential Benefits to Others

Include benefits to society or others.

Others may potentially benefit if oral naltrexone is shown to have some efficacy over PHP alone, as there are not many effective pharmacotherapies for eating disorder. If this medication is shown to have some beneficial effect in this study, the hope is that eating disorder may have another treatment option.

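### The one secondary objective (self-harm and impulsivity) has seven or eight unranked endpoints and no exploratory tier, and section 8.3 undertakes to report only significant differences

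*Combined protocol and SAP*

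**What the plan says.** - **Objective.** Section 1.0, Table 1, has a single secondary objective, which concerns desire to self-harm ("naltrexone on desire to self", broken across lines in the table) and impulsivity ("harm and impulsivity in patients").
- **Endpoints.** Table 1 lists eight: EDE-Q, PHQ-9, GAD-7, ABUSI, BIS/BAS, escalation of care, wish to restart the study article ("level of care, desire to restart") and rate of weight restoration. Section 1.3 opens "Secondary outcomes will include improvement in scores on Eating Disorder Examination Questionnaire (EDE-Q" and lists the same endpoints without the restart item, so seven. Neither list ranks them.
- **What each measures.** Section 1.3 describes ABUSI as "an inventory measuring the desire to self-harm" and BIS/BAS as a measure of impulsivity. The secondary justification cell of Table 1 instead groups BIS/BAS with EDE-Q, GAD-7 and PHQ as measuring other features of eating disorder.
- **Exploratory tier.** The Tertiary/Exploratory row of Table 1 is filled in as none.
- **Analysis.** Section 8.3 compares the arms at three weeks, six weeks and six months, adds within-group comparisons over time, and ends: "Statistically significant differences between each group at each endpoint will be noted and reported". For the outcomes it points to sections 1.1 and 1.2, which name only the ED-15. It gives no significance level, test, order or adjustment.

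**The concern.** Two things combine. First, only two of the listed endpoints measure what the secondary objective asks, by section 1.3's own descriptions, yet all stand at the same level and none is marked as hypothesis-generating. Second, the only reporting commitment is conditional on significance. A list of nominally significant findings drawn from many comparisons, without the null ones beside it, cannot be interpreted, because the reader does not know how many tests produced it.

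At stake is what the pilot hands on. If naltrexone does nothing, a scattered significant result on one scale at one visit is still fairly likely, and it could steer the choice of endpoint for a larger trial. The self-harm and impulsivity question could also go without a clear answer, because nothing says which score at which visit answers it.

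**Working it through.** The documents give no alpha or family-wise error figure, and the sample size (30 per arm, section 8.1) was set for feasibility (section 8.2). There is therefore no figure of the plan's own to reproduce.

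**Inputs from the documents**
- Seven secondary endpoints in section 1.3, eight in Table 1.
- Three comparison times in section 8.3.

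**Assumptions**
- Section 8.3 is meant to cover the endpoints of section 1.3.
- Each test is two-sided at 5%.
- Naltrexone has no effect on any endpoint.
- Test statistics are normal with a common correlation of 0.3, 0.5 or 0.8. The documents give no correlation, so this is a range.

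**Count of tests**
- Narrow: seven endpoints, one visit each, 7 tests.
- Wide: five scales × three visits + two single endpoints (escalation, weight) = 15 + 2 = 17 tests. This omits the restart item, the week 8-9 visit and the within-group comparisons.

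**Independent tests, as an upper reference**
- Either direction, 1 − 0.95^k: k = 7 gives 1 − 0.95^7 = 30.2%; k = 17 gives 1 − 0.95^17 = 58.2%.
- Favouring naltrexone, 1 − 0.975^k: k = 7 gives 16.2%; k = 17 gives 35.0%.

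**Correlated tests.** The chance is one minus the probability that every statistic stays inside ±1.96 (either direction), or that every statistic stays below 1.96 (favouring naltrexone):

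| Tests | Direction | Corr. 0.3 | Corr. 0.5 | Corr. 0.8 |
|---|---|---|---|---|
| 7 | either | 27% | 23% | 15% |
| 7 | favouring naltrexone | 14% | 11% | 7% |
| 17 | either | 49% | 39% | 21% |
| 17 | favouring naltrexone | 25% | 19% | 11% |

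The benchmark for one test is 5% in either direction and 2.5% favouring naltrexone. The directional rates are therefore about 3 to 5.5 times their benchmark for seven tests (7.4/2.5 to 13.7/2.5) and about 4 to 10 times for 17 (10.6/2.5 to 25.4/2.5).

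**Endpoints outside the objective.** The five in section 1.3 other than ABUSI and BIS/BAS, at one visit, give 21%, 18% and 13% in either direction at correlations 0.3, 0.5 and 0.8.

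**After the fix.** Two tests, one score each at one visit, unadjusted and independent: 1 − 0.95² = 9.75%. Holm across the two holds this at 5% or less for any correlation. The first Holm step uses 0.025. With 30 per arm and no dropout, the effect detectable with 80% power is (1.96 + 0.84) × √(2/30) = 0.72 SD at 0.05 and (2.24 + 0.84) × √(2/30) = 0.80 SD at 0.025.

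**The case against.** **The quoted rule may not reach the secondary endpoints.** Section 8.3 cites only sections 1.1 and 1.2, and these name only the ED-15. This stands as a caveat, and the error rates depend on the other reading. The plural reference to outcomes, where the cited sections hold just one, suggests a wrong cross-reference. Read literally, the secondary endpoints have no analysis plan, and the objective still has no rule.

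**Table 1 already separates the scales.** A reader might infer that a chance result on, say, GAD-7 could simply be presented as the answer on self-harm. The documents do not support going that far. The justification cell sets EDE-Q, GAD-7, PHQ and BIS/BAS apart from self-harm, so such a claim would contradict it. What remains is that no rule ties the objective to named endpoints, and that the cell and section 1.3 disagree about BIS/BAS.

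**Section 11.2 is not a success criterion.** Its words "If this medication is shown to have some beneficial effect in this study" might be read as letting any one significant test count as success. They answer a prompt about benefit to society and express a hope. Sections 1.1 and 1.2 define success on the ED-15 alone.

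**It is a pilot.** Formal alpha control over all secondary endpoints is not essential here, and a reader might infer that testing must be gated on the primary. That does not follow. Section 8.3 names no primary visit or test for such a gate to rest on, and a gate would suit a confirmatory trial better. Pilot status does not, however, justify reporting only what is significant. It is a reason to label results as exploratory, which the plan does not do.

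**Conclusion.** The point holds as a shortcoming in labelling and reporting. The secondary objective has no designated endpoints, nothing is marked exploratory, and the stated reporting rule is selective.

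If section 8.3 covers the secondary endpoints at two-sided 5% per test, the chance of at least one false result favouring naltrexone is roughly 7% to 14% on the narrow count and 11% to 25% on the wide one, against 2.5%. In either direction it is 15% to 27% and 21% to 49%, against 5%. These figures rest on an assumed alpha, assumed correlations and the assumed scope of section 8.3. Setting the directional rates against 5% would be the wrong comparison.

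The primary ED-15 claim is not affected. For a 60-person pilot this is a cheap improvement worth making before unblinding, not a flaw that undermines the trial.

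**What to change.** 1. In section 8.3, correct the cross-reference so that it includes section 1.3.
2. In Table 1 and section 1.3, name ABUSI (self-harm) and BIS/BAS (impulsivity) at week 6, the end of treatment, as the endpoints that answer the secondary objective. State the score used for each and apply Holm across the two. Reconcile the Table 1 justification that puts BIS/BAS among other features of eating disorder.
3. Move the remaining secondary endpoints, and the other visits of these two, to the Tertiary/Exploratory row. Make the two endpoint lists agree on the restart item.
4. Replace the last sentence of section 8.3 with: *Between-group differences with 95% confidence intervals will be reported for all outcomes at all time points whatever the p-value; exploratory results are nominal and do not support a claim of efficacy.* This wording also covers the primary outcome, so its reporting is not lost.

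No gate on the primary result is required.

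**Cost.** Edits to three places before unblinding, with no new data, visits or participants. A significant result on another secondary scale could only be called exploratory. Holm slightly lowers power for ABUSI and BIS/BAS: at its stricter step the detectable effect rises from 0.72 to 0.80 SD.
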